Study Rationale:	
BHV-4157 is a glutamate modulating drug that is being developed for eventual commercial use in the treatment of spinocerebellar ataxia (SCA). There is a current Phase IIb/3, double-blind, placebo-controlled study being performed in 140 ambulatory patients with SCA 1, 2, 3, 6, 7, 8, and 10 (ClinicalTrials.gov Identifier: NCT0296089; IND/FDA Orphan Designation 16-5200; Compassionate IND for this proposed study—pending).
 
There is currently no approved medication indicated for SCA.
 
BHV-4157 is a novel tripeptide prodrug of the glutamate modulating agent riluzole. While BHV-4157 has yet to be fully studied in clinical populations, studies with riluzole in populations with ataxia provide support for the therapeutic potential of BHV-4157. Relevant pharmacologic activities of riluzole, such as increasing glutamate transporters (Cvetanovic et al. 2015; Custer et al. 2006) or potential activation of small-conductance calcium-activated potassium channels (Shakkottai et al. 2011) prompted clinical testing. Two well-designed clinical trials (Ristori et al. 2010) and (Romano et al. 2015) demonstrated preliminary safety and robust efficacy of riluzole 50 mg twice a day in patients with SCA. Since BHV-4157 is a prodrug of riluzole, it is expected to have similar therapeutic potential in SCA.
 
BHV-4157 was developed to advance upon the limitations of riluzole that have restricted its broader clinical application. Riluzole tablets have 60% bioavailability, attributed to high first-pass metabolism in the liver. This is thought to be related to metabolism by the heterogeneously expressed CYP1A2 enzyme, which also contributes to the high PK variability associated with riluzole (Greenveld et al. 2001; Sanderink et al. 1997; Martinet et al. 1997). In addition, riluzole is associated with reduced exposure when taken with meals (i.e., a negative food effect), resulting in the guideline to take riluzole within a three hour fasting window (one hour before or two hours after a meal). Riluzole is also dosed twice a day, has dose-dependent effects on liver function tests, and the drug substance itself has other intrinsic limitations including: very low solubility in water, poor oral palatability, pH dependent chemical stability, and intense oral numbness if administered directly to the oral mucosa.
 
In an effort to mitigate the aforementioned limitations of riluzole, several classes of prodrugs were designed, synthesized, and evaluated in multiple in vitro stability assays to predict in vivo drug levels (McDonnell et al. 2012). BHV-4157 is a third generation of prodrug development representing multiple years of chemistry effort with optimized in vivo and in vitro features based on stability while transiting the digestive system, enhanced gastrointestinal absorption, avoidance of first pass metabolism, favorable safety pharmacology, metabolic cleavage in the plasma, enhanced pharmacokinetic properties, and good oral palatability.
 
Based on the preclinical features of BHV-4157, we anticipate the clinical pharmacology to offer favourable properties as compared to commercially available riluzole:
 
 • BHV-4157 is expected to have better oral bioavailability; • BHV-4157 is designed to release riluzole after bypassing first-pass metabolism and thus lowers the overall drug burden to the liver, which may translate into a better safety and tolerability profile, and reduces pharmacokinetic variability.

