-------------------------	--

	
 • BHV-4157 is expected to allow for once daily dosing, thus improving regimen compliance; • BHV-4157 is expected to be readily absorbed in both the fasting and fed states; thus, the prodrug is not anticipated to require any special meal restrictions. In contrast, oral riluzole tablets require a 3-hour window of fasting around the two daily doses. • BHV-4157 will ultimately be formulated as an orally dispersible tablet (Zydis). This formulation will be amenable to patients who have difficulty swallowing. BHV-4157 is expected to have good oral tolerability and palatability when administered sublingually.
Study Design:	
BHV4157-Open is a single center, open study designed to assess safety, tolerability, and efficacy signals in a population of subjects with Cerebellar Ataxia. Subjects will receive oral BHV-4157 (140 mg QD).
 
Dosing will continue for 12 weeks, with subjects being seen every 4 weeks. Subjects will return to the clinic two weeks after discontinuing study medication for a follow-up safety visit. Subjects will be offered an additional 36 weeks of extension treatment (as allowed by the FDA) as long as the PI believes the extension treatment offers an acceptable risk-benefit profile.
 
Subjects entering the Compassionate Extension Phase will undergo visits every 12 weeks up to Week 48. All subjects will undergo a termination visit two weeks after the last dose of study drug.

Subjects:	
Up to 24 male and female outpatient subjects between the ages of 18 – 75, inclusive, with a known or suspected diagnosis of the following specific ataxias: SCA3/dizziness predominant (up to 4 subjects); SCA1, SCA2, SCA3, or SCA6 already taking Riluzole for more than 8 weeks (up to 4 subjects, who will directly switch to BHV4157 at Baseline visit); non-genetic pure cerebellar ataxia (up to 4 subjects); MSA-C (up to 12 subjects).

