--	---

	
(MDRD) Study equation $< 30 \text{ ml/min/} 1.73\text{m}^2$; The MDRD estimation is calculated as follows: eGFR ($\text{mL/min/} 1.73\text{m}^2$) = 175 x (standardized Scr)-1.154 x (Age)-0.203 x (0.742 if female) x (1.212 if Black). [Scr: Standardized serum creatinine]
 
g. Hematologic abnormalities at screening:
 
 i. Hemoglobin $< 10 \text{ g/dL}$; or ii. WBC $< 3.0 \times 10^3/\text{mm}^3$; or iii. Platelet count $< 100,000/\text{mm}^3$; 
h. Human Immunodeficiency Virus (HIV) positive at screening (indicated by positive confirmatory Western Blot);
 
i. HBsAg or HCV positive at screening;
 
j. QTc (Bazett's) and QTc (Fridericia) interval $> 480 \text{ msec}$ at screening and confirmed by repeat measurement or uncontrolled arrhythmia or frequent premature ventricular contraction (PVCs) ($> 5/\text{minute}$) or Mobitz Type II second or third degree atrioventricular (AV) block or evidence of acute or sub-acute myocardial infarction or ischemia. [Note: Subjects with MRI compatible pacemakers or bundle branch block (BBB) and a paced QTc (Fridericia) $< 480 \text{ msec}$ and a stable cardiac status may be enrolled after obtaining a cardiology consult. It must be determined by the consulting cardiologist that the subject's cardiac status is stable and does not pose a risk for participation in the trial.]
 
k. Screening laboratory testing can be done at patient's primary care physician's office up to 6 weeks prior to Screening visit, provided that results are available at time of Screening visit.
 
4. Prohibited Treatments and/or Therapies
 
 a. History of not tolerating treatment with riluzole for any reason b. Treatment with riluzole in the 30 days prior to screening and/or during the study; [with the exception of the switch group of SCA subjects]. c. Prior trial of riluzole treatment of at least 8 weeks duration; [with the exception of the switch group of SCA subjects]. d. Use of chlorzoxazone is prohibited 30 days prior to screening and during the study; e. Use of aminopyridine is prohibited 30 days prior to screening and during the study; f. Use of tricyclic antidepressants and mono-amine-oxidase (MAO) inhibitors are prohibited 30 days prior to screening and during the study; g. Use of any approved treatments for Alzheimer's Disease (AD). Subjects should be free of such medications (donepezil, galantamine, rivastigmine and memantine) for at least 3 months prior to Baseline with no plans to start such medications during the study; or, subjects should be on stable doses of these medications for at least 3 months prior to the baseline visit; h. Use of memantine is prohibited 30 days prior to screening and during the study; i. A new anxiolytic or sleep medication not taken at a stable dose within 30 days prior to screening. Note: Low dose anxiolytic pre-medications prior to diagnostic testing (e.g., MRI) as well as sleep medications taken prn (as needed) are

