Extension Phase:	Subjects completing the initial 12 week open-label administration will be offered and additional 36 weeks of open-label extension treatment (as allowed by the FDA) as long as the PI believes continued open-label treatment offers an acceptable risk-benefit profile.
Drug Administrations:	Subjects will receive oral BHV-4157 (140 mg QD).

Laboratory Assessments and Sample Collection:
	
 • Laboratory Assessments: All laboratory testing should be done fasting and testing will include the following. Laboratory testing designated as Screening can be done up to 12 weeks prior to the Baseline visit: 
 a) Hematology: hemoglobin, hematocrit, red blood cells, white blood cells, differential count and absolute platelet count [Screening, Week 12, Week 24, Week 36, and Week 48]. b) Serum Chemistry: albumin, sodium, potassium, chloride, calcium, AST, ALT, LDH, alkaline phosphatase, GGT, CPK, total protein, total bilirubin, glucose, creatinine, blood urea nitrogen (BUN), uric acid, triglycerides, total cholesterol, HbA1C, P- Amylase or Lipase, TSH, T4, and urine pregnancy testing will be performed at Screening. Urine pregnancy testing will be repeated at Baseline (up to 72 hours prior) and Week 12. AST, ALT, LDH, alkaline phosphatase, GGT, and total bilirubin will be repeated at Week 12, Week 24, Week 36, and Week 48. c) Urinalysis: macroscopic examination, pH, specific gravity, ketones, nitrites, bilirubin, urobilinogen, leukocyte esterase, protein, glucose, and occult blood will be performed at Screening. d) HBsAg, HCV and HIV antibody detection will be performed at Screening 
Any lab value outside of the normal range must be brought to the attention of a physician (Investigator or Sub-Investigator) at the site. The Investigator will indicate whether or not a flagged value is of clinical significance.
 
 • BDNF Blood Sample Collection: N/A • Pharmacogenetic Blood Sample Collection: N/A • Pharmacokinetic Sample Collection: N/A

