Subject Safety:	
Initial 12 week open-drug administration
 
 • Review of subject eligibility before dosing; • Concomitant medication review: At Screening, Baseline, and through the 2-week Post Last Dose; • Physical examination at Screening, Baseline, and Week 12 • Physical measurements and vital signs will be done assessed at Screening, Baseline, and Week 12; • The Beck Depression Inventory (BDI) and The Beck Anxiety Inventory (BAI) will be assessed at Screening, Baseline, and Week 12. The Sheehan Suicidality Tracking Scale (Sheehan STS) will be assessed at Screening and all visits through the 2-Weeks Post Last Dose Visit; • 12-Lead ECG will be done at Screening and Week 12; • Hematology, serum chemistries, and urinalysis at screening. • CBC and Liver Function Tests will be done at Screening and Week 12; • Urine pregnancy testing will be performed on WOCCBP at screening, baseline, and Week 12. Urine pregnancy testing may also be done at the discretion of the Investigator. • Subjects will be monitored throughout the study for adverse events. 
Extension Phase [Week 12 through Week 48]
 
 • Physical examination will be assessed at Baseline/Week 12, Week 24, Week 48, and 2-Weeks Post Dose; • Physical measurements and vital signs will be assessed at Baseline/Week 12 visit through 2-Weeks Post Last Dose; • The Beck Depression Inventory (BDI) and The Beck Anxiety Inventory (BAI) will be assessed at Baseline, Weeks 24, 48 and 2-Weeks Post Dose. The Sheehan Suicidality Tracking Scale (Sheehan STS) will be assessed at Baseline/Week 12 visit through 2-Weeks Post Last Dose; • 12-Lead ECG will be done at Baseline/Week 12. • Hematology, serum chemistry, and urinalysis at Baseline/Week 12.

	
 • CBC and Liver Function Tests will be done at Baseline/Week 12, Weeks 24, 36, 48 and 2-Weeks Post Last Dose; • Urine pregnancy testing will be performed on WOCBP at Baseline/Week 12 and at the discretion of the Investigator. • Subjects will be monitored throughout the study for adverse events.

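### No liver test is scheduled between Screening and Week 12, so all 84 daily doses of a riluzole prodrug precede the first on-treatment liver value

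*Protocol*

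**What the plan says.** Two sections of the protocol give the same liver schedule. Under Subject Safety, for the initial 12 weeks: "CBC and Liver Function Tests will be done at Screening and Week 12". Under Laboratory Assessments and Sample Collection: "AST, ALT, LDH, alkaline phosphatase, GGT, and total bilirubin will be repeated at Week 12, Week 24, Week 36, and Week 48". The only laboratory test that section repeats at Baseline is the urine pregnancy test. It also sets the age limit for the pre-treatment sample: "Laboratory testing designated as Screening can be done up to 12 weeks prior to the Baseline visit".

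On hepatic risk, the Study Rationale says that riluzole "has dose-dependent effects on liver function tests". It expects the prodrug to place less burden on the liver, "which may translate into a better safety and tolerability profile"; this is put forward as an anticipation drawn from preclinical features.

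On visits, Study Design says: "Dosing will continue for 12 weeks, with subjects being seen every 4 weeks". On earlier exposure, the Exclusion criteria (item 4c) rule out: "Prior trial of riluzole treatment of at least 8 weeks duration; [with the exception of the switch group of SCA subjects".

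On what happens to results: "Any lab value outside of the normal range must be brought to the attention of a physician". The extension is offered if the principal investigator judges the balance of risk and benefit acceptable. In the Extension Phase list under Subject Safety, the Week 12 visit doubles as the extension baseline. Liver function tests are a listed safety assessment under Study Endpoints.

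**The concern.** The protocol names a liver effect of the active moiety and then schedules no liver test while that effect could first appear. Adverse events are followed throughout, but a rise without symptoms produces no adverse event report unless someone takes blood. Three consequences follow.

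- **Subject safety.** A subject whose liver tests rise in the first weeks goes on taking 140 mg daily, and no scheduled test would show it before Week 12.
- **The safety data.** With one on-treatment value, the 12-week liver data cannot show a rise that came and went, nor when a rise still present at Week 12 began. A subject who stops before Week 12 may contribute no scheduled on-treatment value: the initial-phase list has no liver test at the visit two weeks after the last dose, and that draw appears only in the extension list.
- **The extension decision.** The first on-treatment sample is drawn at the visit that opens the extension. Nothing requires the result to be read before the investigator makes the risk-benefit judgement, so extension dosing can begin with no on-treatment liver value seen.

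Most subjects bring no evidence of having tolerated riluzole for long. Outside the switch group, a previous course of 8 weeks or more is an exclusion.

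**Working it through.** The plan gives no figure of its own to reproduce. The check is interval arithmetic on the stated schedule.

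**Inputs**

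- Scheduled liver tests to Week 12: Screening and Week 12 (Subject Safety; Laboratory Assessments agrees).
- Maximum age of the Screening sample at Baseline: 12 weeks (Laboratory Assessments).
- Dosing: 140 mg once daily for 12 weeks (Study Design; Drug Administrations).
- Visits: every 4 weeks, hence Weeks 4, 8 and 12 (Study Design). Weeks 4 and 8 are inferred, because the protocol as available has no visit table.
- Enrolment: up to 24 subjects, of whom up to 4 are in the riluzole switch group (Subjects).

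**Current schedule**

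- Doses before the first on-treatment value = weeks × 7 = 12 × 7 = 84.
- Gap between consecutive scheduled tests = age of the Screening sample at Baseline + weeks to the first on-treatment test. Minimum 0 + 12 = 12 weeks; maximum 12 + 12 = 24 weeks. The on-drug part is 12 weeks in every case.
- Subjects outside the switch group, with the groups filled = 24 − 4 = 20.

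**With draws at Weeks 4 and 8**

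| Quantity | Now | With the added draws |
|---|---|---|
| Doses before first on-treatment value | 12 × 7 = 84 | 4 × 7 = 28 |
| Longest on-drug gap up to Week 12 | 12 weeks | 4 weeks |
| Longest gap, last pre-dose to first on-treatment test | 12 + 12 = 24 weeks | 12 + 4 = 16 weeks |
| Extra samples | – | 24 × 2 = 48 at most |

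**A second window.** Exclusion item 3k lets screening laboratory work be done at a primary care office up to 6 weeks before the Screening visit. The time from Screening to Baseline is not stated, so this window cannot be turned into an age at Baseline. The 24-week maximum uses the explicit 12-week limit. The 12-week on-drug gap does not depend on either window.

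**The case against.** The strongest reply is that this is a deliberate and internally consistent choice in a small study with real hepatic safeguards at entry. The protocol excludes active liver disease and significant hepatic intolerance, unstable hepatic disease, AST, ALT, GGT or bilirubin above twice the upper limit, positive hepatitis B or C results, and anyone who has not tolerated riluzole. It requires medical stability at Baseline, judged partly on laboratory results. Adverse events are monitored, abnormal values go to a physician, and unscheduled tests are not barred. These measures lower the risk in the group enrolled. None of them detects a symptomless rise after dosing starts, and the Baseline judgement may itself rest on results 12 weeks old.

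A second objection is that 24 weeks overstates the hazard, since up to half of it is before any drug. That is fair as a reading of drug exposure. The figure that matters for drug-induced injury is the 12 weeks on drug; the earlier weeks affect only how current the comparison value is.

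Third, the protocol gives no incidence, size or onset time for liver-test rises on riluzole, so no one can say from this document how many would be caught. This stands: 84 against 28 doses describes the schedule and is not a risk estimate.

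Fourth, draws at Weeks 4 and 8 leave the pre-dose value up to 12 weeks old at Baseline. This also stands. It limits the remedy without undoing the reduction in the on-drug gap.

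Finally, the silence on reading the Week 12 result before the extension does not show that it would be ignored. That is correct, and the main point does not rest on it.

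**Conclusion.** The concern holds. The two relevant sections agree, so the schedule is fixed and has no liver test from Screening to Week 12. All 84 daily doses of the initial period come before the first scheduled on-treatment liver value, and consecutive tests are 12 to 24 weeks apart, always including 12 weeks on drug. The protocol's own rationale names the liver effect, and the visits needed to close most of the gap already exist.

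This is a weakness in safety monitoring and not an error of calculation. The timing of safety samples by visit belongs in the protocol, so an analysis plan would not cure it. The change should be made; it is inexpensive and improves both subject safety and the liver safety data.

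The conclusion assumes that 4-weekly attendance means visits at Weeks 4 and 8, that the 12-week limit caps the age of the Screening sample, and that subjects dose daily as planned. It makes no claim about how often liver-test rises will occur.

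**What to change.** Amend Laboratory Assessments and Sample Collection and the initial-phase list under Subject Safety so that the repeat liver panel already defined (AST, ALT, LDH, alkaline phosphatase, GGT and total bilirubin) is also drawn at the Week 4 and Week 8 visits. A blood count on the same sample is optional. Add one sentence requiring the investigator to review at least one on-treatment liver result before extension treatment starts; a Week 8 sample makes this practicable without delaying the extension. No hold or stopping threshold is proposed here.

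The cost is a protocol amendment, at most 48 blood samples (two per subject, both fasting), modest laboratory charges, and investigator time to read the results. It needs no new visits or staff.

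If the sponsor also wants a current pre-dose value, a Baseline draw would bring every gap from first dose to Week 12 down to 4 weeks, for at most 24 further samples (24 × 1). This is a worthwhile addition, but the main improvement does not depend on it.

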	
has not been previously done on the study subject and a copy of results is not available for verification.
 
 b. Ability to ambulate 8 meters without assistance (canes and other devices allowed); c. Determined by the investigator to be medically stable at Baseline/randomization as assessed by medical history, physical examination, laboratory test results, and electrocardiogram testing. Subjects must be physically able and expected to complete the trial as designed; d. Minimum of 6 years of education; e. Subjects must have adequate hearing, vision, and language skills to perform interviews as specified in the protocol; f. Subjects must be able to understand and agree to comply with the prescribed dosage regimens and procedures; report for regularly scheduled office visits; and reliably communicate with study personnel about adverse events and concomitant medications; g. Women of childbearing potential (WOCBP) and men must be using an acceptable method of contraception to avoid pregnancy throughout the study and for up to 30 day after the last dose of investigational product in such a manner that risk of pregnancy is minimized. The requisite drug interaction studies to determine the interaction of BHV-4157 with oral contraceptives have not been performed to date. It is therefore not possible to determine the efficacy of oral contraceptives as an effective method of contraception for WOCBP who participation this study. Oral estrogen and progestin hormonal contraceptives as a sole method of contraception are therefore prohibited. It is required that all WOCBP use two methods of contraception for the duration of the study (i.e. beginning at first treatment to 30 days after the last dose of study drug). The two methods should include one barrier method (ex. condom with spermicidal gel, intrauterine devices, cervical cap etc.) and one other method. The other method could include oral contraceptives or another barrier method. h. Women of childbearing potential must have a negative serum pregnancy test at screening and a negative urine pregnancy test within 72 hours prior to first dosing. i. SCA subjects (SCA3/dizziness predominant; SCA1, 2, 3, 6 on Riluzole for more than 8 weeks) will not be limited to Inclusion Criteria of Screening SARA score ≥8 or Score of ≥ 2 on gait subsection of the SARA.

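### No pregnancy test is scheduled after Week 12, although women in the extension take the drug for 36 more weeks at visits that could carry a urine test

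*Protocol*

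**What the plan says.** Two places in the Protocol set the pregnancy-test schedule, and they agree on when it ends.

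- **Laboratory Assessments and Sample Collection:** after the Screening test, "Urine pregnancy testing will be repeated at Baseline (up to 72 hours prior) and Week 12". No later test is listed.
- **Subject Safety, Extension Phase:** "Urine pregnancy testing will be performed on WOCBP at Baseline/Week 12 and at the discretion of the Investigator".

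The same Extension Phase list continues other laboratory monitoring to the end: "CBC and Liver Function Tests will be done at Baseline/Week 12, Weeks 24, 36, 48 and 2-Weeks Post Last Dose".

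Study Design offers 36 further weeks of treatment after the first 12, with visits every 12 weeks to Week 48 and a termination visit two weeks after the last dose.

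Contraception is not left to discretion. Inclusion criterion 3g states: "It is required that all WOCBP use two methods of contraception for the duration of the study", and it carries the obligation to 30 days after the last dose. It adds that "The requisite drug interaction studies to determine the interaction of BHV-4157 with oral contraceptives have not been performed to date" and that "Oral estrogen and progestin hormonal contraceptives as a sole method of contraception are therefore prohibited". The required pair is described as follows: "The two methods should include one barrier method (ex. condom with spermicidal gel, intrauterine devices, cervical cap etc.) and one other method". The next sentence reads: "The other method could include oral contraceptives or another barrier method".

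**The concern.** The Protocol treats pregnancy on drug as a risk to be avoided for the whole of dosing and for 30 days beyond, but its scheduled means of detecting one stops a quarter of the way through the longest possible exposure. The daily dose is the same before and after Week 12 (140 mg), and no reason is given for ending the tests there.

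In the first 12 weeks, discretionary testing is added to fixed tests. In the extension, after the Week 12 test, it replaces them. A subject may use an oral contraceptive as her second method, and the Protocol itself says its efficacy alongside BHV-4157 cannot be determined. She still has a barrier method, so she is not unprotected, but one of her two methods is of unknown reliability.

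What is at stake is late recognition of a pregnancy exposed to an investigational drug. No efficacy endpoint or analysis is affected.

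**Working it through.** No sample-size or error-rate formula applies; the check is arithmetic on the visit schedule.

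**Inputs**

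- Initial dosing: 12 weeks (Study Design).
- Extension dosing: 36 weeks, optional (Study Design; Extension Phase).
- Extension visits: every 12 weeks to Week 48, plus one two weeks after the last dose (Study Design).
- Scheduled pregnancy tests: Screening, Baseline and Week 12 (Laboratory Assessments; Subject Safety).
- Contraception obligation: to 30 days after the last dose (Inclusion criterion 3g).

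**1. The Protocol's own figure.** 12 + 36 = 48 weeks, which matches the stated extension of Week 12 through Week 48.

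**2. Share of dosing after the last scheduled test (extension completer).**

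- Total dosing: 48 × 7 = 336 days.
- After Week 12: 36 × 7 = 252 days.
- Share: 252 / 336 = 75%.

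**3. Length of the gap from Week 12.**

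- To the last dose: 48 − 12 = 36 weeks.
- To the post-dose visit: 50 − 12 = 38 weeks.
- To the end of the contraception period: 36 + 30/7 ≈ 40.3 weeks.

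**4. Visits that could carry a test.** Four visits follow Week 12 for a completer: Weeks 24, 36, 48 and 50.

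| Visit | Pregnancy test scheduled | CBC and liver tests (Subject Safety) | Hematology and liver tests (Laboratory Assessments) |
|---|---|---|---|
| Week 24 | No | Yes | Yes |
| Week 36 | No | Yes | Yes |
| Week 48 | No | Yes | Yes |
| 2 weeks post dose | No | Yes | Not listed |

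Pregnancy tests are scheduled at 0 of 4 visits. Blood tests are scheduled at 4 of 4 by the Subject Safety list, or 3 of 4 by the laboratory section. All four visits exist either way.

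**5. With a urine test at each of the four visits.**

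- The longest on-drug interval without a scheduled test becomes 12 weeks (84 days), down from 36 weeks (252 days).
- Coverage rises from 0 of 4 to 4 of 4 post-Week-12 visits.
- The last visit is 14 days post dose, so 30 − 14 = 16 days of the contraception period (days 15 to 30) remain without a scheduled test.

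**The case against.** The strongest reply is that this is a stated choice, not an oversight. The extension rule is explicit, the two sections agree on it, and the Protocol sets no testing interval that it breaks and gives no reproductive-toxicity data. How often to test women who must already use two methods is a judgement about monitoring intensity. That is fair: the point is a weak design choice, not a contradiction.

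Other safeguards exist: the contraception rule, adverse event monitoring, physical examinations at Weeks 24, 48 and two weeks post dose, and the investigator's risk-benefit view as a condition of extension treatment. They lower the risk or may raise suspicion, but none is a scheduled pregnancy test.

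A 12-week interval might also be called arbitrary, since the Week 4 and Week 8 visits could carry tests too. However, 12 weeks is the on-drug interval the Protocol itself uses between Baseline and Week 12; the proposal extends that standard and does not set a stricter one.

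Finally, the numbers are small. At most 24 men and women aged 18 to 75 are enrolled, the extension is optional and subject to FDA allowance, and WOCBP may be few or none. This limits the expected consequence, but the cost shrinks with it: with no WOCBP, no test is added.

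Separately, the inclusion criteria require a serum test at screening while the other sections specify urine. That mismatch does not bear on testing after Week 12.

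**Conclusion.** The concern holds. For WOCBP in the extension, scheduled testing ends at Week 12 while dosing can run 36 weeks longer. For completers, that is 75% of the 48 weeks with discretionary testing only.

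The 75% assumes the full extension is taken. A woman who stops earlier has a shorter gap, but she too has no scheduled test after Week 12. The schedule facts are certain. The clinical consequence is not quantified, because the Protocol does not give the number of WOCBP and nothing here estimates a pregnancy rate. The change is worth making because it closes a foreseeable safety gap at very little cost; it is not a threat to the trial's results.

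**What to change.** In both Laboratory Assessments and Sample Collection and Subject Safety (Extension Phase), schedule a urine pregnancy test for WOCBP at the Week 24, Week 36 and Week 48 visits and at the visit two weeks after the last dose. Keep discretionary testing as an addition. The post-dose test also covers women who leave the extension early.

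The cost is a short amendment, no new visit, and up to four extra urine tests per WOCBP who completes the extension.
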